### 9.2.2 Non-efficacy monitoring

For each AMP trial, the first non-efficacy analysis will be reported to the DSMB at the first scheduled 6-monthly meeting at which at least a total of 45 HIV-1 infection endpoints have occurred, combined over the three study groups. The analysis is based on all HIV-1 infection endpoints up until the time of data lock, and if this number exceeds 67, then the first non-efficacy analysis would be done based on 67 events and the report provided to the

DSMB by secure means prior to the scheduled DSMB meeting (as noted above).

At each non-efficacy interim analysis PE is estimated with a 2-sided 95% nominal confidence interval using the same method as for the final analysis of PE described in Section 8.1. Cumulative prevention efficacy through time  $t$ ,  $PE(t)$ , will be estimated at time point  $t$  chosen to be the latest possible time point when stable estimation with follow-up data through the Week 80 visit (or earlier if necessary) can be achieved; this is operationalized by defining  $t$  as the maximum time point when 150 participants are observed to be at risk for the primary endpoint in each of the placebo and pooled VRC01 groups. The timepoint  $t$  will be chosen for evaluation of whether the stopping boundary is crossed or not. All times-to-event will be right-censored at the Week 80 visit or earlier following the operational rules summarized in Table 1. As stated in Table 3, the non-efficacy stopping boundary is defined by the 2-sided upper 95% confidence limit for PE being at 40%, where the 95% CI lying below 40% with the lower 95% confidence limit lying below 0% constitutes meeting the guideline for non-efficacy.

The 2-sided 95% confidence intervals for PE, estimated in the same way as described for the final analysis, are reported for sequential monitoring of PE at every DSMB meeting through to the end of the trial.

In addition, a supplemental analysis will estimate the proportional-hazards PE parameter (defined in (3)) with a 2-sided 95% confidence interval and a two-sided p-value for whether proportional-hazards PE differs from unity, following the same statistical procedures described for the final analysis plan (see Section 8.2).

### 9.2.2.1 Unblinded conditional power assessment at an interim analysis

Interim monitoring of PE for non-efficacy will be supplemented with an unblinded conditional power assessment using the actual observed control-group incidence, and the following levels of PE in the future data are assumed:  $PE = 0\%$ ,  $PE = \widehat{PE}$  in the observed data, and  $PE = 60\%$ .

### 9.2.2.2 Estimated prevention efficacy by measured VRC01 neutralization sensitivity

The analyses specified in Section 8.3.1 will be reported at interim analyses that included non-efficacy monitoring.

### 9.2.3 High efficacy monitoring

The 2-sided 95% confidence interval for PE used for non-efficacy monitoring is also used for high efficacy monitoring, where it is compared to  $PE = 70\%$  instead of  $PE = 40\%$  as a

stopping boundary. High-efficacy monitoring is conducted at each interim analysis at which non-efficacy analysis is conducted.

#### **9.2.4 Rationale for starting non-efficacy/high efficacy monitoring at at least 45 total infections**

Freidlin, Korn, and Gray (2010) suggested beginning non-efficacy monitoring as soon as a point estimate of PE equal to zero would correspond to the nominal 95% confidence interval of a hazard ratio based efficacy parameter under a Cox proportional hazards model just barely ruling out the design alternative (PE = 40% in the AMP trials). This approach implies starting the non-efficacy monitoring at the 67th total infection in each AMP trial. However, based on protocol projections of accrual and incidence, between about 60 and 100 total HIV-1 infection events are expected in each trial, for PE varying over the range 0% to 60%. Therefore it would not be unlikely that no non-efficacy interim analysis would occur if the Freidlin, Korn, and Gray (2010) recommendation were strictly followed. Moreover, a high efficacy analysis would not occur, as its timing is synchronized to the non-efficacy monitoring timing, which could be problematic if the PE is very high. Accordingly, the monitoring starts at at least 45 infections, which is judged to be large enough to have reasonable precision and small enough to make it likely that some non-efficacy/high efficacy interim analyses would occur during the trial. Note that if the first non-efficacy interim analysis occurred at 45 total infections, then stopping for non-efficacy, which would occur if the nominal 2-sided 95% confidence interval lies below 40%, would correspond to a negative PE estimate. This is an advantageous property in that a result of early non-efficacy would be an unambiguous result about absence of prevention efficacy.

### **9.3 Monitoring of the Use of PrEP**

The use of oral FTC/TDF as PrEP (either off-study or provided in the study) may impact study outcomes (e.g., by lowering HIV-1 incidence rendering a loss of study power). Dried blood spot (DBS) samples will be used for assessment of quantitative concentrations of intracellular TFV-DP.

Prevalence of oral FTC/TDF will be reported both as any detectable use and estimated effective use. Estimated percentages of person-years at-risk during any detectable FTC/TDF use and during inferred effective FTC/TDF use will be reported. We summarize how inferred effective use is measured. Current knowledge about PrEP in MSM indicates consistent use of at least 4 doses a week is required to achieve substantial levels of protection. The lower quartile of simulated tenofovir diphosphate (TFV-DP) levels in DBS at 4 doses per week is 719 fmol/punch (Castillo-Mancilla et al., 2013). In iPrEx OLE, the protective levels of TFV-DP in DBS were quantified as 700 fmol/punch (Grant et al., 2014), that is, there were no infections at visits where TFV-DP concentration was 700 fmol per punch or greater. Current knowledge about PrEP in women indicates consistent use of 6–7 doses a week is required to

achieve protection. The lower quartile of simulated TFV-DP levels in DBS at 6 doses per week is 1064 fmol/punch (Castillo-Mancilla et al., 2013). In the HVTN 704/HPTN 085 study we will use 700 fmol/punch as the cut-off to define effective PrEP use based on the lower quartile cited above. For the HVTN 703/HPTN 081 study we will use 1,000 fmol/punch since current knowledge suggests that at least 6 doses of PrEP per week is required for effective PrEP use in women based similarly on the lower quartile. Ongoing work with calibration of DBS from directly observed dosing studies may refine these thresholds. PrEP use measures will be reported by arm to the DSMB; in addition both the OC and the protocol team leadership will see pooled estimates of FTC/TDF use.

HVTN 704/HPTN 085 collects and stores DBS samples at every study visit, whereas HVTN 703/HPTN 081 collects and stores DBS samples at pre-specified DBS sample collection days. The sample collection days can vary by study site; however, it is expected that the collection days will occur once per month. Furthermore, in order to tune the precision of PrEP use estimation, the frequency of collection may be increased. While the storage and collection differs by protocol, the selection of stored samples to assay will be similar. We refer to the method of selecting participant samples for assaying DBS samples for prospective monitoring of PrEP as the DBS sampling plan.

At a given calendar time  $T$  (e.g., a fixed date prior to a scheduled DSMB meeting), we are interested in the population-level parameter, percent person-years at-risk for HIV on effective PrEP use between initiation of DBS storage, and time  $T$ . Definition of this parameter makes the assumption that we have an assay readout from stored samples that accurately measures effective PrEP use as a binary outcome at the time the sample was drawn; importantly it does not require an accurate measurement of effective PrEP use the day before or for any period of time earlier than the sampling day. In addition to estimating percent person-years on effective PrEP use we define a similar parameter, percent person-years exposed to detectable PrEP using the lower limit of quantitation (LLOQ) of the DBS assay.

Define the target parameter of interest as

$$\Phi(T) = \frac{\int_{T_0}^T p(t) E[Y(t)] dt}{\int_{T_0}^T E[Y(t)] dt}$$

where  $T_0$  is the time since the first person enrolled after DBS storage commenced,  $p(t)$  is the percent of participants on effective PrEP use at time  $t \in [T_0, T]$ , and  $E[Y(t)]$  is the expected number of participants with DBS storage at-risk for HIV at time  $t$ .

We estimate  $\Phi(T)$  based on the binary PrEP use readout from the DBS assay and the DBS sampling plan. Let  $i$  ranging from 1 to  $N$  index study participants and let  $j$  ranging from 1 to  $M_i$  index participant serum collection dates that are sampled for assaying. For each sample collected, we have an indicator  $x_{ij}$  of effective PrEP use which is only measured if the DBS sampling indicator,  $\Delta_{ij}$ , is equal to 1. The estimated percent person-years on effective

Table 5: Estimated rates of PrEP use and estimated percent person-years on effective PrEP use

Number of DBS specimens collected over the 1 st batch period	$N_1$
Number of DBS specimens assayed over the 1 st batch period	$N_2$
Proportion of assayed specimens with TFV-DP above LLOQ (95% CI)	$N_3/N_2$ (x.xx, x.xx)
Proportion of assayed specimens with TFV-DP above effective use threshold* (95% CI)	$N_4/N_2$ (x.xx, x.xx)
Percent person years on detectable PrEP through date T=xx (95% CI) #	$\widehat{\Phi}(T)_d$ (x.xx, x.xx)
Percent person years on effective PrEP through date T=xx (95% CI) #	$\widehat{\Phi}(T)_e$ (x.xx, x.xx)
Repeat through N th batch period	

\*threshold defined by study (700 fmol/punch MSM+TG, 1000 fmol/punch sub-Saharan African Women)

# $\widehat{\Phi}(T)_d$  is an estimate of the target parameter of interest based on measured TFV-DP above the LLOQ. Similarly,  $\widehat{\Phi}(T)_e$  is based on TFV-DP above the study specific threshold for effective PrEP use.

PrEP use from the initiation of PrEP monitoring time  $T_0$  until time  $T$  is defined as

$$\widehat{\Phi}(T) = \frac{\sum_{i=1}^N \sum_{j=1}^{M_i} \Delta_{ij} x_{ij} \pi_{ij}^{-1} P_{ij}}{\sum_{i=1}^N \sum_{j=1}^{M_i} P_{ij}}$$

where the sampling probability,  $\pi_{ij}$ , and person-years,  $P_{ij}$ , are defined below.

Let  $k$  ranging from 1 to  $K$  index the DBS sampling plan collection intervals  $[T_0, T_1]$ ,  $(T_1, T_2]$ ,  $\dots$ ,  $(T_{K-1}, T_K]$  where the right endpoint of each interval is a sample collection date (with  $T_K \equiv T$ ) and define  $\mathcal{T}_k$  as the  $k^{\text{th}}$  interval. Let  $t_{i1} < t_{i2} < \dots < t_{iM_i}$  be the sampling times in  $[T_0, T]$  for the  $i^{\text{th}}$  participant and define  $t_{i0}$  as the maximum of  $T_0$  and the  $i^{\text{th}}$  participants enrollment time. The DBS sampling plan determines which samples, collectively across participants, will be assayed for PrEP use. Define the set of samples,  $S_{ij}$ , as all samples collected during the same collection interval  $\mathcal{T}_k$  as the sample  $i, j$ . That is,  $S_{ij} \equiv \{i', j' | t_{i'j'} \in \mathcal{T}_k \text{ for } k \text{ s.t. } t_{ij} \in \mathcal{T}_k\}$ . Define the sampling probability as

$$\pi_{ij} \equiv \frac{\sum_{i', j' \in S_{ij}} \Delta_{i'j'}}{|S_{ij}|}$$

where  $|S_{ij}|$  is the number of samples in set  $S_{ij}$ . Define person-years,  $P_{ij}$ , as  $t_{ij} - t_{i(j-1)}$ . Note that our parameter of interest can be defined and estimated for the entire study cohort, as well as for sub-regions (e.g., North America for the HVTN 704/HPTN 085 study). We will report bootstrap 95% confidence intervals for  $\Phi(T)$ .

The same approach is used for point and confidence interval estimation of the percent person-years exposed to detectable PrEP use.

An example of PrEP use report statistics are shown in Table 5.

[figure not shown]

Figure 1: PrEP use Monitoring under three PrEP use scenarios (40%, 20% and 10% per person year) in the HVTN704/085 trial. For 6-monthly intervals shown on the x-axis all samples assayed to date are used to estimate PrEP use prevalence from the beginning of monitoring until that time using the estimator described in Section 8.4. Below each date is the total number of samples that would be assayed according to the simulation study. Estimates are shown as a dots of varying color intensity corresponding to the three PrEP use scenarios. Corresponding color bands are used to show the 95% bootstrap confidence interval for each estimate.

### 9.3.1 Simulation Study for PrEP Monitoring

A simulation study was conducted to help determine the number of DBS samples that should be collected and assayed a simulation study was run. For a simulated AMP trial, the PrEP monitoring plan was implemented based on the following assumptions: 1) Enrollment falls randomly between Monday and Friday; 2) Follow-up visits follow the visit schedule exactly; 3) Missed visits are distributed uniformly at a rate of 10%; 4) Dropout is 10% per person year based on an exponential distribution; 5) HIV-infection is 3% for HVTN 704/HPTN 085 (or 5.5% for HVTN 703/HPTN 081) per person year based on an exponential distribution; and, 6) Initiation of DBS sample collection begins as of November 1, 2016 in both protocols. PrEP use was simulated at various constant rates among trial participants and participants are assumed to be either on (or off) PrEP during the entire trial. Simulation results for each trial are presented for the number of samples collected spaced at 6 month intervals. The

[figure not shown]

Figure 2: PrEP use Monitoring under three PrEP use scenarios (20%, 10% and 1% per person year) in the HVTN703/081 trial. For 6-monthly intervals shown on the x-axis all samples assayed to date are used to estimate PrEP use prevalence from the beginning of monitoring until that time using the estimator described in Section 8.4. Below each date is the total number of samples that would be assayed according to the simulation study. Estimates are shown as a dots of varying color intensity corresponding to the three PrEP use scenarios. Corresponding color bands are used to show the 95% bootstrap confidence interval for each estimate.

intervals are spaced such that the last collection time point is approximately 3.5 months prior to the next DSMB meeting to allow the intracellular TFV-DP assay to be run and a report generated. In this simulation, all samples collected per protocol HVTN703/HPTN081 version 2.0 would be assayed. For the HVTN704/HPTN085 trial, all samples collected the clinic business day closest to the 15th of each month would be assayed. Simulation results are shown in Figures 2 and 1.

The simulation study results show that by the time 200 samples have been selected the confidence intervals around the estimate of PrEP use are reasonably tight and by the time 500 samples have been selected the extra gain in precision as more samples are assayed becomes limited. However, continuing to assay samples over the course of the trial will allow estimation of temporal trends in PrEP use. The simulation also shows that when PrEP prevalence is very low the bootstrap confidence interval is unlikely to provide proper

coverage.

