4.6.6 Rationale for the HIV-1 incidence assumptions

The assumption of 3% annual HIV-1 incidence in the control group accommodates background PrEP use by assuming incidence is decreased by two parameters: (1) the fraction of person-years at-risk during which PrEP is used; and (2) the level of efficacy of PrEP during PrEP use. Figure 4-5 shows the annual HIV-1 incidence in the control group as a function of these two factors, for a scenario where the annual HIV-1 incidence is 4% in the absence of any PrEP use. Based on HVTN 505 data (US participants only) through September 30, 2014, the annual HIV-1 incidence in the control group was 2.0% (95% CI 1.5%—2.7%) and in the vaccine and control groups pooled was 2.1% (95% CI 1.5%— 2.8%). From HVTN 505, based upon case report form (CRF) collection of PEP/PrEP med usage and responses to questions regarding usage posed on the 'anonymous' (to the site) ACASI questionnaire through June 1, 2014, 5% of participants reported ever using PrEP. In HVTN 505 the amount of person-years at risk during periods of PrEP use was likely well below 5%, and, therefore, the 2.1% annual incidence is a reasonable assumption for the baseline rate without PrEP. In particular, assuming 1.6% annual control incidence in the US and Switzerland (which is expected if 27% of person-years at risk are during PrEP use and PrEP efficacy is 90% during use) and assuming 5% annual control incidence in South American participants [7], (with 5% of person-years at risk during PrEP use and 90% PrEP efficacy during use), 44% of participants enrolled at South American sites would yield the assumed 3% annual control incidence rate.

[figure not shown]

Figure 4-5 Annual HIV-1 incidence in the control group assuming 4% annual HIV-1 incidence in the hypothetical scenario of no PrEP use, under different levels of PrEP use and levels of PrEP efficacy

Higher than expected use of PrEP would be reflected in lower than expected annual incidence rates, as shown in Figure 4-5. As shown in Figure 4-2, the trial would still provide enough statistical information to be powered to detect highly relevant prevention efficacy effect sizes if annual incidence rates are lower than we have estimated here due to higher than expected use of PrEP.

4.7 Power for the secondary analysis comparing HIV-1 incidence between the 10 mg/kg mAb group versus the 30 mg/kg mAb group

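### SAP 9.3 plans only a bootstrap interval for person-years on PrEP, which under-covers when few assayed samples are positive and collapses to 0% to 0% when none is; no fallback is given

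*SAP*

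**What the plan says.** SAP 9.3 estimates the percent of person-years on effective PrEP "based on the binary PrEP use readout from the DBS assay and the DBS sampling plan". For the interval it says "We will report bootstrap 95% confidence intervals for" that parameter. For the lower threshold it adds: "The same approach is used for point and confidence interval estimation of the percent person-years exposed to detectable PrEP use". The parameter can be estimated for the whole cohort "as well as for sub-regions (e.g., North America for the HVTN 704/HPTN 085 study"), and PrEP measures go to the DSMB by arm. Neither the type of bootstrap nor the resampling unit is stated.

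SAP 9.3.1 describes the supporting simulation and ends by conceding that "when PrEP prevalence is very low the bootstrap confidence interval is unlikely to provide proper" coverage. The text then turns to futility monitoring in 9.4, with no fallback method or low-count rule.

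The simulated prevalences differ by trial. For this trial: "PrEP use Monitoring under three PrEP use scenarios (40%, 20% and 10% per person year) in the HVTN704/085 trial". For the sister trial under the same SAP: "PrEP use Monitoring under three PrEP use scenarios (20%, 10% and 1% per person year) in the HVTN703/081 trial".

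**The concern.** The plan reports a defect in its own interval and leaves the interval in place. The defect lies at low use, where an honest upper limit is the useful quantity: the DSMB needs to know how much PrEP use the data still allow. An interval that is too narrow, or has zero width, overstates certainty about low use. In by-arm tables it could also make a chance difference look real, for example one arm at 0% (0% to 0%) beside another with a few positives.

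**Working it through.** The SAP gives no coverage figure, so there is none to reproduce. I checked its qualitative finding in three steps.

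**Inputs.** Sample counts of 200 and 500 are the two benchmarks in SAP 9.3.1. One arm's third of 200 is 200/3 ≈ 67. A South American share of 0.44 × 200 = 88 uses the 44% enrolment share in Protocol 4.6.6. Prevalences are 1% (the lowest in the SAP's simulation), 10% to 40% (the HVTN 704/HPTN 085 scenarios), and 5%, because Protocol 4.6.6 works one incidence scenario for South America "with 5% of person-years at risk during PrEP use".

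**Step 1: no positives.** The estimator is Φ̂(T) = Σ Δᵢⱼ xᵢⱼ Pᵢⱼ/πᵢⱼ ÷ Σ Pᵢⱼ, with xᵢⱼ equal to 0 or 1. If every assayed xᵢⱼ is 0, the numerator is 0 in every resample, whether specimens or participants are resampled. Percentile, basic and normal-SE bootstrap intervals are then all 0% to 0%. Coding the estimator confirmed this for 200 samples, 500 samples, and 200 assayed out of 4,000. A Clopper-Pearson interval with zero positives runs from 0% to 5.36% (n = 67), 1.83% (n = 200) or 0.74% (n = 500).

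The chance of zero positives is (1 − p)ⁿ. At p = 1%:
- n = 200: 0.99²⁰⁰ = 13.4%
- n = 88: 0.99⁸⁸ = 41.3%
- n = 67: 0.99⁶⁷ = 51.0%
- n = 500: 0.99⁵⁰⁰ = 0.7%

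**Step 2: exact coverage.** With x positives among n independent, equally weighted samples, the bootstrap distribution is Binomial(n, x/n)/n. The percentile limits are its 2.5% and 97.5% quantiles. Coverage is the sum of Binomial(n, p) probabilities over those x whose limits include p.

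| Prevalence | n | Bootstrap | Wilson |
|---|---|---|---|
| 1% | 88 | 57.5% | 94.1% |
| 1% | 200 | 86.5% | 94.8% |
| 1% | 500 | 95.5% | 96.2% |
| 5% | 67 | 84.8% | 95.0% |
| 5% | 88 | 92.6% | 95.7% |
| 10% | 200 | 95.8% | 95.6% |

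For n = 200 and 500 at 10%, 20% and 40% prevalence, bootstrap coverage is 95.5% to 95.8%.

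**Step 3: where the loss comes from.** At 1% with 200 samples, zero positives account for 13.4 points of miss and large counts for 0.1, leaving 86.5%. At 5% with 67 samples, a single positive also misses: the upper limit is 3/67 = 4.5%, below 5%. Zero or one positive has probability 14.6%, and large counts add 0.6%, leaving 84.8%.

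**The case against.** The strongest objection is relevance. For HVTN 704/HPTN 085 the SAP simulated only 10% to 40%, where the bootstrap performs well. The 5% for South America is one worked scenario; Protocol 4.6.3 uses 25%, 30%, 40% and 50% for Peru and Brazil. The estimate is also cumulative. Taking 2,700 participants, 25 visits each and samples from one of about 21 clinic days a month (an assumed figure), and ignoring dropout and the start date of collection, 2,700 × 25/21 ≈ 3,200 samples are assayed by the end, or about 1,070 per arm. At 1% prevalence coverage is already 95.5% by 500. This stands, and it limits the point to early or subdivided reports and to the sister trial.

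A second objection is that no decision depends on the interval. The enrolment and futility guidelines in SAP 9.4 use infection counts and estimated efficacy. With 0 of 88 positive the Wilson upper limit is 4.2%; at 90% PrEP efficacy that removes 0.042 × 0.9 = 3.8% of incidence, or 3.0% down to about 2.9%. This also stands.

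A reader might infer that every interval in the PrEP report is a bootstrap. The documents do not show that: SAP Table 5 also gives 95% intervals for the raw proportions of specimens, with no method named. Its counts would also show the DSMB that a zero came from so many specimens. That softens the 0% to 0% entry but does not correct it.

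What does not stand is that disclosure is enough. Stating the weakness in 9.3.1 tells the analyst neither when to distrust the interval nor what to report instead.

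**Conclusion.** The point holds, as a minor one. The bootstrap is the only interval named for the two person-years parameters. The SAP itself doubts it at very low prevalence, and with no positive samples it is necessarily 0% to 0%. Under the stated assumptions the loss ranges from about 8 points of coverage (1%, 200 samples) to about 37 (1%, 88 samples), and it is negligible at 10% or more with 200 samples, or at 1% with 500 or more.

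The coverage figures rest on a percentile bootstrap and on independent, equally weighted samples. The SAP specifies none of these. Its simulation has each participant on or off PrEP throughout, so repeat samples are clustered; that would reduce the effective sample size and probably worsen low-prevalence coverage, but I have not computed by how much. The zero-positive result needs none of these assumptions.

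It would be tempting to conclude that PrEP monitoring in this trial is unreliable, or that the efficacy result is at risk. The documents support neither. The exposure is early, by-arm or sub-region reports here and low-use reports in HVTN 703/HPTN 081. The primary analysis and the stopping guidelines do not use this interval.

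**What to change.** Add a low-count rule to SAP 9.3. When few assayed samples in a reported cell are positive (for example fewer than 10), replace the bootstrap with a Wilson or Clopper-Pearson interval on the weighted proportion.

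The effective sample size needs a stated conservative rule, because within-participant correlation cannot be estimated when every readout is zero. Cap it at the number of distinct participants assayed, reduced further by the Kish factor for unequal weights. One way to do both: sum each participant's weights, wᵢ = Σⱼ Δᵢⱼ Pᵢⱼ/πᵢⱼ, and take n_eff = (Σ wᵢ)²/Σ wᵢ², which cannot exceed the number of participants assayed. This works with zero positives. Otherwise keep the bootstrap and state that it resamples participants. Name the interval method for the specimen proportions in Table 5 at the same time.

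The cost is a few lines of code and wider intervals at low prevalence. The threshold of 10 is a convention, and interval width may jump slightly where the method switches.
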